5. REMOVAL OF SUBJECTS FROM STUDY TREATMENT OR ASSESSMENT

5.1. Discontinuation from Study Treatment

A subject's double-blind treatment may be discontinued for any of the following reasons:

- Worsening of disease (Note: If a subject discontinues double-blind treatment at any time starting with the Week 12 assessment, the subject may be eligible to enter the APD334-303 OLE study [Section 5.1.1])
- Adverse event that in the judgement of the Investigator and/or Medical Monitor the subject should not continue study treatment
- Subject noncompliance with the protocol or study treatment that is considered significant by the Medical Monitor
- Investigator decision
- Withdrawal by subject or parent/guardian (if applicable)
- Lack of efficacy
- Lost to follow-up
- Study termination by Sponsor
- Other, non-adverse event

A subject's double-blind treatment must be discontinued for any of the following reasons:

- Decline in PFT values (FEV₁ and/or FVC) below 50% of the predicted values
- Confirmed diagnosis of clinically significant macular edema
- Confirmed diagnosis of active TB
- Subjects who have a cardiovascular treatment-related symptomatic event (eg, chest pain, dizziness, palpitations, lightheadedness, shortness of breath, or syncope) associated with reduction of the heart rate or associated with clinically relevant ECG changes at any time during the 4-hour monitoring period on Day 1 or Day 2 (as applicable) (Section 9.4.2.1)
- Subjects who have not met the discharge criteria on Day 1 after ≥ 4 hours of extended monitoring, or Day 2 by 4 hours post-dose (Table 3).
- Pregnancy (Section 9.9.10)
- Suspected drug induced liver injury as defined by the 2009 FDA Guidance for Industry (FDA 2009)

- ALT or AST > 8 × ULN
- ALT or AST > 5 × ULN for > 2 weeks
- ALT or AST > 3 × ULN and (total bilirubin > 2 × ULN or international normalized ratio > 1.5)
- ALT or AST > 3 × ULN with the appearance of fatigue, nausea, vomiting, right upper quadrant pain or tenderness, fever, rash, and/or eosinophilia (> 5%)

Because transient fluctuations of ALT or AST are common, and progression to severe drug-induced liver injury or acute liver failure is uncommon, automatic discontinuation of study treatment upon finding a greater than 3 × ULN elevation of ALT or AST may be unnecessary. If a drug-induced liver injury is identified, refer to Appendix 6 for guidance.

Subjects who discontinue treatment prematurely, regardless of the reason, should be instructed to return for an ET visit within 7 days of the last administration of study treatment (Appendix 1, Table 6) and before initiation of any new treatments to complete all of the ET assessments. If a subject discontinues due to pregnancy, they are not required to complete the endoscopy. If the ET visit is within 4 weeks of the last sigmoidoscopy and biopsy, these procedures do not need to be repeated.

If the ET visit is ≥ 2 weeks of the last administration of study treatment, the 2-Week Follow-Up visit is not required; however, the 4-Week Follow-Up visit should be scheduled and completed. If the ET visit is ≥ 4 weeks of the last administration of study treatment, the 4-Week Follow-Up visit is not required unless the absolute lymphocyte count (ALC) is not within normal limits.

If treatment discontinuation is considered an adverse event, refer to Section 9.9.9.3 for AE/SAE reporting guidance.

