9.8.5. Efficacy-Related Biomarkers

Samples for biomarker assessments will be collected according to the Schedule of Assessments (Appendix 1, Table 6). Blood, tissue, and stool samples will be analyzed by the central or specialty laboratory. Details for collection, processing, and storage will be provided in the Laboratory Manual. Residual samples will be stored and may be used for additional analyses if the subject has granted consent where allowed by the regulatory authorities and local ethics committees.

C-reactive protein (CRP): CRP is an acute phase protein expressed by hepatocytes in response to inflammatory cytokines and will be assessed using a hs-CRP assay. Investigators will be blinded to the hs-CRP results during the treatment and follow-up periods.

Fecal calprotectin: Fecal calprotectin is a complex consisting of calcium-binding proteins. It is expressed by activated neutrophils (and to a lesser extent by macrophages and monocytes) and fecal levels correlate with the number of neutrophils in the gut. It is used as a biomarker of intestinal inflammation. Investigators will be blinded to the fecal calprotectin results during the treatment and follow-up periods.

[figure not shown]
Lymphocyte counts: Etrasimod is believed to modulate lymphocyte trafficking resulting in a reduction in peripheral lymphocyte count and lymphocyte availability for recruitment to sites of inflammation. During the treatment period, the Investigator will be blinded to the white blood cell (WBC) and differential counts during the treatment and follow-up periods. During the treatment period, WBC differential results will be assessed by an unblinded Medical Monitor (not providing direct medical oversight of study conduct). If either of the following occur, the unblinded Medical Monitor will notify the Investigator with additional instructions.

- ANC < 1000 cells/μL
- ALC < 200 cells/μL

If the ANC is confirmed below the 1000 cells/μL limit, the Investigator will be requested to closely monitor for serious infection and institute appropriate follow-up at his or her discretion.

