 - Maximum aspartate aminotransferase (AST) versus same-day total bilirubin
 - Maximum alanine aminotransferase (ALT) versus same-day total bilirubin

The eDISH plots above will be repeated with adjustment for elevated Baseline.

- Incidence of hepatic enzyme elevations by visit and overall post baseline
 - $> 1 \times, 2 \times, 3 \times, 5 \times, 8 \times, 10 \times, 20 \times$ upper limit of normal (ULN) elevation in ALT
 - \rightarrow 1 ×, 2 ×, 3 ×, 5 ×, 8 ×, 10 ×, 20 × ULN elevation in AST
 - $> 3 \times, 5 \times, 10 \times, 20 \times$ ULN elevation in either ALT or AST
 - \rightarrow 1 ×, 1.5 ×, 2 ×, 3 × ULN elevation in total bilirubin
 - \rightarrow 1 ×, 1.5 ×, 2 ×, 3 ×, 5 ×, 8 × ULN elevation in ALP
 - $\rightarrow 1 \times, 2 \times, 3 \times, 5 \times, 8 \times \text{ULN elevation in GGT}$
 - $> 3 \times ULN$ elevation in either ALT or AST and $> 1.5 \times ULN$ elevation in total
 - bilirubin
 - $> 3 \times ULN$ elevation in either ALT or AST and $> 2 \times ULN$ elevation in total
 - bilirubin

- $> 3 \times \text{ULN}$ elevation in either ALT or AST and $> 1.5 \times \text{ULN}$ elevation in ALP
- \sim 3 × ULN elevation in either ALT or AST in temporal association with

treatment-emergent nausea, vomiting, anorexia, abdominal pain, or fatigue identified by PT, where temporal association is defined as ± 14 days of onset date from the time of elevation.

If both central and local assessments of total bilirubin are available on the same day, the central result will take precedence over the local result in the eDISH plot. If the maximum AST, ALT, GGT, or ALP assessment occurs at 2 different dates, the assessment with the higher accompanying Bilirubin value will be used. Two versions of the eDISH plots will be presented, with one showing values as multiples of ULN, and the other one showing values as multiples of ULN, or participant's baseline, whichever is higher.

Participant's laboratory assessments at all timepoints will be listed in chronological order. Values outside of the laboratory reference range will be flagged. Values obtained from local laboratory will be flagged. A listing of lymphocytes and neutrophils over time in participants who ever had lymphocytes $< 0.5 \times 10^9/L$ or neutrophils $< 1 \times 10^9/L$ will also be provided.

Pregnancy Tests

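### The eosinophilia-only trigger of the mandatory liver stopping rule (Protocol 5.1) has no specified route to an investigator who is blinded to the differential (Protocol 9.8.5)

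*Protocol*

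**What the plan says.** **Stopping rule.** Protocol Section 5.1 introduces its compulsory list with "A subject's double-blind treatment must be discontinued for any of the following reasons". One entry is ALT or AST above 3 × ULN "with the appearance of fatigue, nausea, vomiting, right upper quadrant pain or tenderness, fever, rash, and/or eosinophilia (> 5"%). The same section adds that "automatic discontinuation of study treatment upon finding a greater than 3 × ULN elevation of ALT or AST may be unnecessary", so at that enzyme level the accompanying feature decides.

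**Blinding.** Section 9.8.5 states that "the Investigator will be blinded to the white blood cell (WBC) and differential counts during the treatment and follow-up periods". It also says that "WBC differential results will be assessed by an unblinded Medical Monitor (not providing direct medical oversight of study conduct").

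**Reporting duty.** Section 9.8.5 continues: "If either of the following occur, the unblinded Medical Monitor will notify the Investigator with additional instructions". Two items follow. One is "ANC < 1000 cells/μL" and the other is ALC below 200 cells/μL.

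**SAP.** Section 6.3.2.1 plans a display of ALT or AST above 3 × ULN in temporal association with "treatment-emergent nausea, vomiting, anorexia, abdominal pain, or fatigue". Eosinophilia, fever and rash are not in that list.

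**The concern.** The stopping rule and the blinding rule pull apart on one data item. The investigator, who applies Section 5.1, sees ALT and AST but not the differential. The unblinded Medical Monitor sees the differential but has no written instruction to look at eosinophils, to set them beside ALT and AST, or to tell the site.

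At stake is a mandatory safety criterion. A participant could satisfy it on central laboratory values that the trial already collects and remain on study treatment, with everyone following the text. A site that ordered its own blood count to fill the gap would also see the lymphocyte count. Section 9.8.5 expects etrasimod to lower that count, and it is among the results being blinded.

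**Working it through.** There is no sample size, power or event figure to reproduce. The check sets the passages side by side.

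**1. When does eosinophilia decide?** The bullet is an and/or list, so there are two cases with ALT or AST above 3 × ULN:

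- (a) A listed sign or symptom is present (fatigue, nausea, vomiting, right upper quadrant pain or tenderness, fever, rash). The investigator can see this, and the rule works.
- (b) Eosinophils above 5% are the only accompanying finding, and none of the other enzyme criteria in Section 5.1 is met: not above 8 × ULN, not above 5 × ULN for more than 2 weeks, bilirubin not above 2 × ULN and international normalized ratio not above 1.5. Stopping is still mandatory, and it turns on the differential alone.

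**2. In case (b), what could carry the eosinophil result to the investigator?**

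| Place | What it provides | Specified route for eosinophils? |
|---|---|---|
| Protocol 9.8.5, notification | Two triggers, ANC < 1000 and ALC < 200 cells/μL, introduced by the word either | No |
| Protocol 9.8.5, release of blinded values | Conditional on at least one ALC < 200 cells/μL | No |
| Protocol Table 5, footnote on unblinded review | Instructions to the site for significant lymphopenia; one cell type is redacted | No |
| Protocol 9.9.8, local laboratory results | Recording of local results that change management; no local differential is required | No |
| Protocol Appendix 6, liver work-up | Albumin, CK, fractionated bilirubin, GGT, PT/INR, bile acids, alkaline phosphatase and others | No differential listed |

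**3. Could redaction explain the gap?** This is unlikely for the notification list, because either points to two items and both are legible. In the Table 5 footnote, whatever the hidden cell type is, the stated instruction to the site still concerns lymphopenia.

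**4. Are the data already there?** Yes. Table 6 schedules the CBC with differential and the laboratory panel together at Weeks 2, 4, 8, 12, 16, 24, 32, 48 and 52. What is missing is the link between the two results, not a sample.

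**5. Would the analysis show such cases?** Partly. SAP 6.3.2.1 tabulates ALT and AST elevations and lists every laboratory value chronologically with out-of-range flags, so a reader could match the results by hand. No planned table links them. The symptom display shares fatigue, nausea and vomiting with Section 5.1, has abdominal pain where Section 5.1 has right upper quadrant pain or tenderness, adds anorexia, and omits fever, rash and eosinophilia. The markedly abnormal cell-count summary covers lymphocytes and neutrophils only.

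**The case against.** The strongest reply is that the practical gap is narrow, and much of that reply stands. Case (a) works as written. The other enzyme criteria and investigator-decision discontinuation remain available in Section 5.1, and Appendix 6 asks for closer monitoring above 3 × ULN. The unblinded Medical Monitor does see the differential, and no passage forbids reporting it. Local results are foreseen. A reader might infer that this part of the rule can never operate, or that every such case would be missed. The documents do not support that: they leave the route unspecified, not closed.

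The scope of the blinding is also not uniform. Section 9.8.5 covers differential counts in general. Section 9.9.8 refers only to total WBC and ALC being handled under 9.8.5. The Table 5 footnote names total WBC, neutrophils, lymphocytes and a redacted type. That footnote is not exhaustive either, since it omits the ANC trigger that 9.8.5 plainly contains, so its silence on eosinophils should not carry much weight. The Laboratory Manual and the DMC Charter, which might say more, are not part of the documents reviewed.

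On the SAP, a reader might infer that the planned outputs conceal these cases. They do not, because the listings allow reconstruction, and fever or rash reported as adverse events would appear in the adverse event tables. Nothing obliges a descriptive display to reproduce the stopping list.

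A reader might also infer that the criterion is met more often on etrasimod, because lowering lymphocytes raises eosinophils as a percentage of WBC. The documents give no eosinophil data, so that remains conjecture.

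What the reply does not supply is a written path for case (b).

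**Conclusion.** The point holds in a limited form. When eosinophils above 5% are the only feature accompanying ALT or AST above 3 × ULN, and no other liver criterion is met, the protocol states a mandatory stop but specifies no way for the deciding result to reach the person who must act. This is a conflict between two stated rules, not merely missing detail.

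The number affected is probably small and cannot be estimated from the documents, which give neither the frequency of such enzyme elevations nor any eosinophil distribution. The conclusion assumes that the Section 9.8.5 blinding of differential counts includes eosinophils, and that no document outside the protocol and SAP supplies the route. If sites can in fact see eosinophils, the conflict reduces to unclear wording about what is blinded. No position is taken on which clinical rule is right.

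**What to change.** Reconcile Protocol Section 5.1, the lymphocyte-count part of Section 9.8.5, the Table 5 footnote and Appendix 6, so that the criterion as the sponsor intends it can be acted on while the blind is kept. The text should also settle whether eosinophils fall within the blinded results. The clinical rule and the mechanism are for the sponsor to decide.

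The cost is a text change in the protocol and in the unblinded reviewer's instructions. The differential is already collected and already reviewed unblinded, so no new sample is needed. There is one small downside: any message to a site that rests on eosinophils alone discloses a blinded differential finding, so its wording needs care.

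Optionally, align the SAP 6.3.2.1 display of ALT or AST above 3 × ULN with the reconciled Section 5.1 list, so that one planned table links the results that now have to be matched by hand. That is one changed table row, and it would still be useful if the conduct change came too late to affect participants.

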5.1.1. Discontinuation from Double-Blind Treatment for Disease Worsening

Starting with the Week 12 assessment, subjects whose UC condition in the opinion of the Investigator has not improved or has worsened, compared with baseline (Week 0/Day 1), may be eligible to enroll in the OLE study (Study APD334-303) provided their ES is ≥ 2 and they meet one of the following entry criteria:

- RB subscore ≥ 2 at 2 timepoints at least 7 days and no more than 14 days apart
- RB + SF subscores ≥ 4 at 2 timepoints at least 7 days and no more than 14 days apart
- RB subscore ≥ 2 or RB + SF subscores ≥ 4 (in any order) at 2 timepoints at least 7 days and no more than 14 days apart

For subjects discontinuing prior to Week 52, an endoscopic evaluation is required to confirm eligibility for the OLE. An endoscopy should be performed upon the appearance of UC symptoms but no more than 14 days after the second timepoint for symptom criteria above. A proctosigmoidoscopy does not need to be repeated if performed within the last 4 weeks.

The Day 1 visit of the OLE study must occur within 14 days of the last on treatment visit of this study. In the event there is a gap between the last on treatment visit and W0/D1 of the OLE, the subject should continue their double-blind study treatment from Study APD334-210 until the day before the W0/D1 visit.

5.2. Discontinuation from the Study

Subjects may be discontinued from the study at any time for any of the following reasons:

- Withdrawal by subject or parent/guardian
- Deviation/noncompliance with the study protocol that in the judgement of the Investigator and/or Medical Monitor the subject should not continue study treatment
- Study termination by Sponsor
- Lost to follow-up
- Death
- Other

A subject may withdraw from the study at any time for any reason without prejudice to their future medical care by the physician or at the institution. If a subject withdraws consent, no further evaluation should be performed, and no additional data should be collected. The Sponsor may retain and continue to use any data collected before such withdrawal of consent. The Investigator should make a reasonable attempt to document the specific reason why consent was withdrawn.

In the event that a subject fails to attend any follow-up visits, all reasonable efforts will be made to contact the subject to ensure that he/she is in satisfactory health. All contacts and contact attempts must be documented in the subject's file.

5.3. Subjects Lost to Follow-Up Prior to Last Scheduled Visit

A subject will be considered lost to follow-up if he or she repeatedly fails to attend a scheduled visit and is unable to be contacted by the study site.

The following actions must be taken if a subject fails to attend a required onsite, offsite, virtual, or hybrid visit (Section 9.6):

- The site must attempt to contact the subject and reschedule the missed visit as soon as
 possible and counsel the subject on the importance of maintaining the assigned visit
 schedule and ascertain whether or not the subject wishes to and or should continue in
 the study.
- Before a subject is deemed lost to follow-up, the Investigator or designee must make every effort to regain contact with the subject (where possible, 3 telephone calls and if necessary, a certified letter to the subject's last know mailing address or local equivalent methods). These contact attempts should be documented in the subject's file

Should the subject continue to be unreachable, he/she will be considered to have withdrawn from the study.

5.4. Premature Termination of the Study

The Sponsor has the right to terminate this study at any time. Reasons for terminating the study may include, but are not limited to, the following:

- The incidence or severity of adverse events in this or other studies indicates a
 potential health hazard to subjects
- Subject enrollment is unsatisfactory
- Upon request of health authorities

The Sponsor will notify Investigators if the study is placed on hold or if the Sponsor decides to discontinue the study or development program. Health authorities and Independent Ethics Committees/Institutional Review Board (IECs/IRBs) will be informed about the termination of the study in accordance with applicable regulations.

The Sponsor has the right to replace a study site at any time. Reasons for replacing a study site may include, but are not limited to:

- Excessively slow recruitment
- Poor protocol adherence
- Inaccurate or incomplete data recording
- Non-compliance with the ICH guideline for GCP.

6. STUDY TREATMENTS

6.1. Treatments Administered

Subjects will be randomly assigned to 1 of 2 treatment groups (etrasimod or placebo) in a 2:1 ratio. Study treatment is outlined in Table 1.

Table 1: Study Treatment

Study treatment name:	Etrasimod	Placebo	
Dosage formulation:	2 mg tablet	Matching tablet	
Unit dose strength/dosage level:	1 tablet once daily	1 tablet once daily	
Route of administration:	By mouth	By mouth	
Packaging and labeling:	Study treatment will be provided in 40 cc, induction-sealed, high-density polyethylene bottles with child-resistant screw caps. Each bottle will be labeled as required per country requirement. These bottles should be stored at 15 to 25°C (59 to 77°F).	Study treatment will be provided in 40 cc, induction-sealed, high-density polyethylene bottles with child-resistant screw caps. Each bottle will be labeled as required per country requirement. These bottles should be stored at 15 to 25°C (59 to 77°F).	

6.2. Investigational Study Treatment

The active pharmaceutical ingredient in etrasimod tablets is APD334 L-arginine (the arginine salt of (R)-2-(7-(4-cyclopentyl-3-(trifluoromethyl)benzyloxy)-1,2,3,4-tetrahydrocyclopenta[b]indol-3-yl)acetic acid), which is an off-white to light-brown solid with an aqueous solubility of approximately 1.38 mg/mL at pH = 8.9 and 30°C. APD334 L-arginine is manufactured, packaged, tested, and released in compliance with cGMP.

The drug product is a blue, round, biconvex, plain, immediate-release, film-coated tablet. Etrasimod tablets are supplied in the dosage strength (based on etrasimod free-acid content) of 2 mg.

The placebo tablet formulation is composed of excipients (microcrystalline cellulose NF, Ph. Eur.; mannitol USP, Ph. Eur.; sodium starch glycolate NF, Ph. Eur.; magnesium stearate NF, Ph. Eur.; and Opadry[®] II Blue 85F90951). Placebo tablets are identical in appearance to the active-drug tablets as described above.

6.3. Dosage and Administration

One tablet is to be taken each day (with water, either with or without food). Tablets should be taken at approximately the same time each day, preferably in the morning. On study visit days, subjects should wait and take their dose after blood draws for PK and after all pre-dose assessments and procedures have been completed. The time of PK sample collection and last dosing prior to the PK sample should be documented in the electronic case report form (eCRF).

6.3.1. Instructions for Missed Dose(s)

Subjects should be instructed that if they forget to take a dose, they can take the dose within 8 hours of the normal dosing time; otherwise, they should take their next dose at the regular time on the following day. If the subject vomits the tablet, he/she should be instructed not to take another tablet on the same day, but to take the next dose at the regular time on the following day. Missed doses should be recorded in the subject's electronic diary (eDiary), as indicated in the Schedule of Assessments, Table 6. Subjects should be instructed to contact the Investigator if they miss more than 2 consecutive doses.

Subjects who do not take the study treatment for ≥ 2 consecutive days within the first week of treatment or for ≥ 7 consecutive days after the first week of treatment must contact the Investigator to discuss treatment re-initiation. The subject must take the next dose of study treatment at the study site, and the in-clinic cardiac monitoring as outlined in Section 9.4.2.1 should be performed.

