6.3.2. Dose Interruptions

If the Investigator deems it necessary to withhold study treatment, temporary withholding is permitted for up to 6 days without obtaining prior approval from the Medical Monitor. If study treatment interruption ≥ 7 days is required for a medical reason, the Investigator must contact the Medical Monitor.

The first-dose monitoring as outlined in Section 9.4.2.1 should be performed any time a subject misses study treatment as follows:

- ≥ 2 consecutive days within the first week of treatment, or
- ≥ 7 consecutive days after the first week of treatment

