8.4. Study Treatment Accountability

At each visit, previously dispensed study treatment tablets will be collected by the Investigator or qualified individual and compliance assessed. Subjects will record tablet self-administration daily in an eDiary that will be reviewed at each treatment visit by study site staff.

The Investigator must maintain adequate records documenting the receipt, use, loss, or other disposition of the study treatment. To ensure adequate records, all study treatment supplies will be accounted for and will be monitored by counting of unused tablets from individual bottles returned by the subject at each visit (Appendix 1, Table 6).

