9.4.2. Treatment Period

After randomization, the 12-Week Treatment Period of the study will begin (Appendix 1, Table 6). A study visit window of \pm 3 days is permitted at each visit beginning with Week 2/Day 15 (PFT and OCT assessments have a window of \pm 7 days). After the Week 12 visit, a study visit window of \pm 7 days is permitted. Study visits should be scheduled for the morning.

The subscores for SF and RB are derived from the subject eDiary entries. On visits when MMS is calculated, these subscores are derived using the scores from the 3 most recent consecutive days within the 7 days prior to the day of bowel preparation (excluding the day of bowel preparation), averaged and rounded to the nearest integer. If 3 consecutive days are not available, then the average of the 2 most recent consecutive days within the 7 days will be used.

On visits without endoscopy, the SF and RB subscores are derived using the scores from the 3 most recent consecutive days within the 7 days prior to the date of visit, averaged and rounded to the nearest integer. If 3 consecutive days are not available, then the average of the 2 most recent consecutive days within the 7 days will be used.

It is recommended that procedures are performed in a consistent order and at approximately the same time of day for each visit. Below is the recommended sequence of events:

- Questionnaire administration
- Adverse event review
- Vital signs
- 12-lead ECG (as indicated in the Schedule of Assessments, Appendix 1, Table 6)
- Physical examination
- EIMs (as indicated in the Schedule of Assessments, Appendix 1, Table 6)
- PFT (as indicated in the Schedule of Assessments, Appendix 1, Table 6)
- OCT (as indicated in the Schedule of Assessments, Appendix 1, Table 6)
- Blood sample collection for laboratory tests and pre-dose PK sampling

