All treatment discontinuations should be discussed with the Medical Monitor. ECG, electrocardiogram

Cardiac Monitoring Upon Treatment Re-Initiation Following Dose Interruption

Subjects should undergo the same First Dose Cardiac Monitoring procedures as the original treatment initiation when study treatment dosing is re-initiated after interruption for:

- ≥ 2 consecutive days within the first week of treatment
- ≥ 7 consecutive days after the first week of treatment

Holter recording will not be repeated for treatment re-initiation.

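### In week 1, the call trigger that participants are to be told (Protocol 6.3.1) comes one dose later than the trigger for monitored re-initiation

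*Protocol*

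**What the plan says.** Protocol 6.3 sets once-daily dosing: "One tablet is to be taken each day".

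Protocol 6.3.1 then gives two rules on when a participant contacts the site.

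- The first paragraph covers what participants are to be told. A dose missed beyond the 8-hour catch-up window is skipped, and dosing resumes at the usual time the next day. It adds: "Subjects should be instructed to contact the Investigator if they miss more than 2 consecutive doses". It does not distinguish week 1 from later weeks.
- The second paragraph sets the re-initiation rule. It applies to "Subjects who do not take the study treatment for ≥ 2 consecutive days within the first week of treatment", or for 7 or more consecutive days after that. These participants have to contact the Investigator, and "The subject must take the next dose of study treatment at the study site", with in-clinic cardiac monitoring.

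Two other sections give the same monitoring thresholds (2 days in week 1, 7 days afterwards). Section 6.3.2 introduces them with "The first-dose monitoring as outlined in Section 9.4.2.1 should be performed any time a subject misses study treatment as follows". Section 9.4.2.1 says "Subjects should undergo the same First Dose Cardiac Monitoring procedures as the original treatment initiation".

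On detection, Section 8.4 says "Subjects will record tablet self-administration daily in an eDiary that will be reviewed at each treatment visit by study site staff". Under Section 9.4.2 and the Schedule of Assessments, the first scheduled visit after Day 1 is Week 2, Day 15 ± 3.

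**The concern.** The two contact rules in 6.3.1 disagree at one point: exactly 2 consecutive missed days in the first week. The second paragraph then requires a call and a monitored on-site dose. The sentence specifying what participants are told does not prompt a call until a third dose is missed, and the same paragraph has them resume at the usual time the next day. A participant who has been given only that paragraph would restart at home and would be following what they were told.

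What is at stake is a cardiac safety step. Section 1.3 lists bradycardia at the first dose and atrioventricular block among events reported with this drug class. Section 9.4.2.1 requires at least 4 hours of in-clinic observation after the first dose, with discharge and discontinuation criteria, and requires it again after a 2-day gap in week 1. That repeat depends on the participant calling before taking the next tablet. If the call is not made, the next planned check is the eDiary review at the Week 2 visit, which can record the lapse but cannot prevent it.

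**Working it through.** The plan states no figure to reproduce. The check is a comparison of integer thresholds and a count of days.

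**Inputs**

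- Dosing: 1 tablet a day, so 1 missed day = 1 missed dose (6.3).
- Call trigger that participants are to be told: more than 2 consecutive doses (6.3.1, first paragraph).
- Trigger for mandatory contact and monitored restart: at least 2 consecutive days in week 1, at least 7 afterwards (6.3.1, second paragraph; the monitoring thresholds are the same in 6.3.2 and 9.4.2.1).
- Next scheduled visit: Day 15 ± 3, that is Day 12 to Day 18 (9.4.2; Schedule of Assessments).

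**Threshold comparison**

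- Told to call: smallest whole number above 2 = 3 missed doses.
- Week-1 requirement: 2 missed doses. Difference = 3 − 2 = 1 dose, so the prompt is late.
- After week 1: requirement at 7, prompt at 3. Difference = 7 − 3 = 4 doses, so the prompt comes first and there is no conflict.

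**Cases affected**

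The Day 1 dose is given on site. Taking the first week as Days 1 to 7, gaps of exactly 2 days inside it, and the time from restart to the next scheduled visit, are:

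| Missed days | Restart day | Days to earliest visit (Day 12) | Days to latest visit (Day 18) |
|---|---|---|---|
| 2–3 | 4 | 12 − 4 = 8 | 18 − 4 = 14 |
| 3–4 | 5 | 12 − 5 = 7 | 18 − 5 = 13 |
| 4–5 | 6 | 12 − 6 = 6 | 18 − 6 = 12 |
| 5–6 | 7 | 12 − 7 = 5 | 18 − 7 = 11 |
| 6–7 | 8 | 12 − 8 = 4 | 18 − 8 = 10 |

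That is five patterns. The visit follows the restart by 4 to 8 days at the earliest and 10 to 14 days at the latest. For participants brought back for a monitored Day 2 dose, the first row drops out because that dose is taken on site.

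**Effect of aligning the wording**

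With a week-1 call trigger of 2 or more missed doses, the difference becomes 2 − 2 = 0.

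**The case against.** The strongest reply is that the two rules can both be followed. A prompt to call at more than 2 missed doses does not forbid a call at 2. The specific mandatory rule follows in the next paragraph, under a heading that presents the whole subsection as instructions. The correct week-1 threshold appears in three sections. Sites are trained on the protocol before study activities begin (12.1), and the Investigator is responsible for instructing participants correctly on how to take treatment (6.6). The harm also requires that participants were told only the earlier sentence, which the documents do not show.

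There are partial safeguards too. Participants leave on Day 1 with written instructions on when to return and a 24-hour number for cardiovascular symptoms (Table 3). Those with a low heart rate or a prolonged PR interval are excluded (4.2). Anyone needing extended Day 1 monitoring has a monitored second dose. The eDiary is completed daily, and compliance may be reviewed virtually (9.6).

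Much of this stands. The requirement is not missing from the protocol, the intended threshold is clear, and no failure has been shown. The defect is a misalignment of wording; the 2-day threshold itself is not in question.

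It does not rescue the sentence. Participants act on what sites tell them, and the sentence saying what to tell them carries the later trigger with no week-1 exception. No scheduled visit falls between Day 1 and Week 2 for participants not recalled on Day 2, and nothing in the protocol ensures that a 2-day gap is noticed before the restart. The other safeguards lower the consequence of an unmonitored restart but do not replace the monitoring the protocol requires.

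**Conclusion.** The point holds as a narrow error in a safety instruction. For week 1, the call trigger participants are to be told is one dose later than the trigger for monitored re-initiation. It should be corrected.

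Its reach is limited to exactly 2 consecutive missed days within the first week. The conclusion rests on once-daily dosing, on reading the first week as Days 1 to 7, and on sites taking participant instructions from the sentence that prescribes them. How often such gaps occur cannot be derived from the documents, so no expected number of unmonitored restarts can be given. Whether participant-facing materials already carry the stricter rule is also unknown.

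**What to change.** Change the one sentence in Protocol 6.3.1, for example to:

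> Subjects should be instructed to contact the Investigator, before taking another tablet, if they miss 2 or more consecutive doses in the first week of treatment, or more than 2 consecutive doses thereafter.

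Then check the participant-facing materials against it. Sections 6.3.2 and 9.4.2.1 already carry the intended threshold and need no change. The cost is one sentence and that check. Dosing, the visit schedule and the analysis are unaffected.
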